All daily video lessons will be posted on the Canvas site, and participants will receive weekly email reminders to view them, at their convenience. Specifically, videos will be posted, by week, in the order they are listed in the syllabus (e.g., video 1 on day 1, then video 2 on day 2). Caregivers are not under pressure to "keep up" with daily viewing; the program allows participants to view the videos when they are able and as often as they wish. Each daily lesson follows the same pattern: (1) Greeting by hosts (2) Slide presentation of educational content (3) caregiving vignettes (a telenovela-type portrayal of a wife and daughter helping to guide the days of a husband living with dementia; the vignettes were written and directed by the Co-Is and played by amateur actors whom we coached) or guest lecture (4) Recap of key points. The video lessons are 6-20 minutes in length, and they will remain available to participants for two weeks after program's end.

Wait List Attention Control Group Condition and Participation. The attention control condition consists of video and text materials on exercise, diet, and healthy living drawn from the NIA Go4Life program. While these materials provide important and beneficial information, we believe they will not affect our postulated key mediators (mood, mastery and care recipient quality of life). They will provide equal attention, but should not confound the trial. The same number of brief modules as employed in Tele-Savvy (36) will be provided over the course of six weeks; videos will emerge on Canvas site weekly in a manner similar to the Tele-Savvy condition described above. Likewise, navigator will send attention control participants weekly reminder e-mails to log into Canvas and view daily videos. All attention-control participants will convene weekly for a videoconference that will mirror Tele-Savvy videoconference in format and length but will differ in content. Specifically, attention control videoconferences will not contain any information on caregiving strategies, but rather will center on the application of healthy living strategies. A standard structure of each videoconference will be employed by attention-control facilitators: (1) Facilitators greet and check in with each of the caregivers; (2) coaching and debriefing (e.g., hearing how (after the first week) caregivers did with the homework, answering questions and/or responding to feedback about the week's material; (3) review of key points and concepts from the week's video sessions and introduction of new material; (4) reports on any activities that caregivers may have implemented based on the Go4Life materials; (5) provision of homework assignments and adjournment.

Usual Care. Those randomized to this group will be encouraged to continue to receive care for the person living with dementia through whatever arrangement had been in place. Since this group will represent a sort of natural history of caregiving, we will not, with one exception, ask them to restrict any activity they might undertake to seek care for the person or information for themselves. The exception we will request is that, during the 6-month period, they not enroll in an extended caregiver education program. If, in the course of these 6 months, they participate in support groups, visit education web sites, attend informational seminars and/or consult with their health care providers, that will be fine. These are all part of the natural history.

Approximately four months after initial data collection, attention-control and usual care participants will be contacted to schedule their participation in Tele-Savvy which will begin 6 months after their baseline assessment. Their Tele-Savvy experience will be exactly the same as that described above (**Immediate Participation Group Procedures**). These participants will be offered the opportunity of another practice session with Vidyo and Canvas prior to the beginning of Tele-Savvy.

Category	Instrument	Instrument Description	Psychometrics
Baseline Only PLWA Cognitive Status	Informant Questionnaire on Cognitive Decline in the Elderly (IQCODE),	A 16-item rating scale (can be informant completed) not contaminated by education	Correlates well with dementia diagnosis; predicts dementia dx as well or better than the MMSE. ¹⁰⁹⁻¹¹⁰
Demographic Information	Demographic sheet Caregiving History	SES, PLWA information, length of caregiving, co-residence with recipient.	Study-developed form (Baseline only)
PLWA ADLs	Lawton ADL/IADL scale	13-item scale elicits caregiver assessment of PLWA ADL and IADL functioning	Interrater reliability between .87-.91 ¹¹¹
[Caregiver Vars] Appraisal: Stress	Perceived Stress Scale	14-item Likert-type questionnaire; higher scores reflect higher perceived stress	Internal consistency ranges reported at 0.84 or higher. ¹¹²

Depression	Center for Epidemiological Studies-Depression	A 20 item Likert scale scored 0-3 with somatic and psychological subscales	Alpha=.85 for general population; validity well-established ⁹⁸
Anxiety	State-Trait Anxiety Inventory	A 20-item 4-point Likert scale is sensitive to changes in transitory anxiety	STAI state sensitive reliability reported at .94 ⁹⁹
Burden	the Zarit Burden Inventory (ZBI),	A 22-item 4-point Likert scale, widely used in caregiving studies	Used in multiple studies with well-established validity ¹¹³
Dyadic Relationship	Dyadic Relationship Scale	11-item scale assesses dyadic strain and dyadic interaction perceived by caregiver	Caregiver alphas = .84 and .85 ¹¹⁴
Coping	Ways of Coping Scale	A 42-item scale with 4-point Likert responses identifies emotion- and problem-focused coping responses	Used in multiple studies with well-established validity ¹¹⁵
Caregiver Mastery	Pearlin Mastery, Loss, and Competence	6 brief (3-6 item) Likert scales assessing mastery and loss dimensions	Alpha coefficients from .71-.92. ¹⁰⁰
Caregiver Skill	Caregiver Assessment of Behavioral Skill	17-item self-report assessment of behavioral management skills	Chronbach alphas from 0.75-0.94 with good validity ¹¹⁶
Caregiver Reward	Positive Appraisal of Care Scale: Consequential Gain	6-item subscale providing caregiver self-rating of benefits and positive experiences of caregiving	Cronbach's alpha 0.84 for the Consequential gain sub-scale. Established validity. Test-retest reliability 0.86 (p<0.01). ¹¹⁷
Caregiver Self-Care	Mindful Self-Care Scale Sub-scales	Sub-scales related to supportive relationships (5 items); self-compassion and purpose (6); mindful relaxation (6); clinical (6); and general (3) [26 items total]	Cronbach's alpha 0.89 for the total 33-item scale (excluding sub-scales Clinical and General); 0.83 for Self-Compassion and Purpose sub-scale; 0.77 for Mindful Relaxation sub-scale. Construct validity established preliminarily. ¹¹⁸
Caregiver Health	Self-rated Health	1-item questionnaire	Test-retest reliability 0.92 ¹¹⁹
[PLWA Variables] Quality of Life	Quality of Life Scale in Alzheimer's Disease	Assesses QOL in 13 domains on a 1-4 point Likert scale. Used as a self-report and surrogate-report instrument	Good internal consistency (Cohen's $\alpha=.86$) and inter-rater reliability (Cohen's $K>.70$). ¹²⁰
Behavioral and Psychological Symptoms in Dementia	Revised Memory and Behavior Problem Checklist	A 22-item Likert scale instrument that assesses patient behaviors and caregiver responses to them	Reliabilities of .84-.90 are reported for behavior and reaction. ¹⁰¹
Care Recipient Mood	Neuropsychological Inventory Questionnaire	12 item inventory assessing severity of mood states or behaviors reflecting mood	Test-retest correlations between total symptom and distress scores in 15 subjects were 0.80 and 0.94, respectively (P< 0.0001 for both). ¹²¹

Data Collection. Data will be collected at baseline and at four subsequent points (months 3, 6, 9, and 12). Each data collection event will follow the same procedure used with the baseline interviews. The Navigator will establish the appointment for the Vidyo interview, and the research specialist, blinded to condition, will conduct the interview. The data collection schedule allows for a direct comparison of outcome measures between groups (at 3 and 9 months); it allows for an examination of prolonged effects (at 9 and 12 months) in the immediate participation group; and it allows for pooling of data across both groups to examine the mediating effects of mastery on distal outcomes in caregivers and PLWD and to compare effects across racial/ethnic groups. Qualitative evaluation interviews will occur at T2 and T3 for a sub-sample of immediate and T4 and T5 for a sub-sample of attention control subjects.

III. G. Variables and Measures. The table above delineates the battery of standardized instruments we will employ; these have well-established psychometric properties (reliability, validity), are used extensively with dementia caregivers, and have been used previously in the *Savvy Caregiver* trials.

As depicted in the figure below, there is a link between our theoretical model and the measures used to test it. Most data will be gathered through the regular interviews, some data will be obtained from self-reported evaluations that caregivers will complete through forms posted on the Canvas site (for example, through logs on the Canvas site in which caregivers report caregiving behaviors they have enacted). After each program, caregivers will be asked, in phone or Vidyo interviews conducted by project investigators, to evaluate the program, indicating what they did/did not like, what did/did not work, how the intervention was helpful or not, and how they would change it. Blackboard will allow us to monitor adherence, dosage and intensity of the

[figure not shown]
intervention. We will be able to track, for each participant, which daily videos were viewed, when they were viewed and in what pattern (e.g., daily or in a batch), and how often. Attendance in the videoconferences will be recorded. We will also document any indications – through participant complaints or the Navigator's log – of participant burden (e.g., complaints voiced during interviews or need to split interviews over multiple sessions) and reports of barriers to participation (e.g., CGs unable to join call, quality of audio/video).

Data Management and Analysis Plan Data will be entered at the time of each interview directly into the dedicated project tablet computer and saved on Emory's secure REDCAP platform. All data entry screens are set up in REDCAP and, where possible, include data delimiters (i.e., skip patterns, valid range limits) to ensure correctness and minimize missing data. Data will be exported into SPSS weekly and syntax run for cleaning, further data verification and file concatenation.

Data integrity checks. After each cohort data-gathering point, all data will be merged in SPSS for scale computation, aggregation, and inferential analysis. In preliminary analyses, descriptive statistics and frequency distributions will be examined to identify outliers and ensure integrity of merged files. For all multi-item scales, internal consistency will be examined using Cronbach's alpha and associated statistics (e.g., item-total correlations, alpha if item deleted). Formal test-retest/inter-rater reliability coefficients will be computed as data are concatenated.

Analytic approach. Preliminary analyses will examine baseline differences among completers and non-completers and by study arm (immediate/attention control/usual care) as a randomization check using means/SDs/Inter-quartile range and t-tests for continuous variables and counts/percentages and N-Par/Chi-Square tests for categorical variables. The association of predisposing factors (demographics, CG history, relationship and care recipient status at baseline) with baseline data as well as change in outcomes over time will be examined using goodness of fit, variance analysis, or correlational techniques depending upon measurement characteristics of variables involved. Where significant baseline associations are detected, these potential confounders will be controlled in subsequent tests of major hypotheses through use of covariates/model adjustments.

Aims 1, 2 and 3 (a). Our primary aims are concerned with assessing the effect of the Tele-Savvy program for reducing or retarding the burden, depression, and anxiety of Alzheimer's family caregiving, promoting the quality of life of persons with Alzheimer's (BPSD, agitation; Quality of Life; affect), and enhancing caregiver mastery. We will employ multi-level mixed effects models (MLM) with random (participant) and fixed (cohort) effects to test linear (and non-linear) trajectories of change for the intervention groups and model group X time and group*time interactions. To compare the Tele-Savvy intervention to the attention control and usual care groups, the first 3 time points will be used to test for differences between the 3 group longitudinal trajectories. Additionally, we will combine the intervention effects for the three groups across the main 3 time points from just before receipt of the intervention to immediately after the intervention to the 1st follow-up time point (T1-to-T2-to-T3 for the immediate group and T3-to-T4-to-T5 for the attention control and usual care groups respectively). These combined time points will be referred to as cT1, cT2, cT3. If there are significant differences between or among the 3 groups at the time point immediately prior to receipt of the intervention (cT1), these "baseline" effects will be included and adjusted for in the final model. Overall time effects will be assessed as well as planned post hoc comparisons for immediate effects (cT1 to cT2), longer term effect (cT1 to cT3) and sustained effects (cT2 to cT3). Sidak Type-I error rate adjustment (which has higher power than Bonferroni) will be applied for the multiple pairwise time point comparisons.¹²² Additionally, longer term sustained effects will be captured for the immediate Tele-Savvy group using the additional follow-up times at T4 and T5 for this group. The proposed study design has the advantage of capturing 3 "baseline" time points for the wait-list attention control and usual care groups which will provide an excellent opportunity to evaluate what if any potential "placebo" effects there may be from being enrolled in this type of study.¹²³ These initial

data captured at T1-T2-T3 for the delay group will also be used to evaluate any potential decline occurring during this time period. All model assumptions will be tested; grand mean centering used to help combat multicollinearity between variables; and standard diagnostic tests and influence statistics used to test the distributions of the residuals. MLM models utilize all available data for all participants at each time point and have the advantage of adjusting for the missing data over time, where repeated measures ANOVAs do not. Further covariate predictors of missingness over time will be included to additionally adjust for these confounders¹²⁴ To aid in final interpretation we will include the 95% confidence intervals around means by intervention group and time period. SPSS v.22 will be used for all analyses at the 5% significance level.¹²²

Aim 3(b). To test the mediating effect of mastery on Aim 1 & 2 outcomes, we will employ the PROCESS add-on module for SPSS¹²⁵ which includes performing the combined approaches of Baron and Kenney, the Sobel test, as well as semi-parametric estimation and testing of the Sobel test through bootstrapping. The focus will be on both the immediate (T2 for immediate Tele-Savvy group and T4 for attention control and usual care groups pooled together) and sustained (T3 for immediate Tele-Savvy group and T5 for attention control and usual care groups pooled together) effects of Tele-Savvy on the mediating measure of mastery on the Aim 1 and Aim 2 outcomes of caregiver burden, depression, anxiety, and dyadic relationship and PLWD BPSD, agitation, mood, and quality of life. These indirect/mediation effects will also be tested and evaluated using structural equation modeling via AMOS v.22.¹²⁶

Exploratory Aim. All subjects will eventually participate in Tele-Savvy, and we will be able to assess program impact on the key caregiver and care recipient measures to test whether the program had similar or different effects across racial/ethnic groups (African American, Caucasian, and Latino/Hispanic). We plan to use the ANCOVA technique to conduct this analysis, using race/ethnicity as the covariate of interest. We expect to conduct a similar analysis to examine differences in impact on rural versus urban caregivers. As our enrollment table indicates, we expect a 20:65:15 African American:Caucasian:Latino subject distribution. The qualitative interviews of participants will enable us to explore the extent to which Tele-Savvy meets caregivers' needs, regardless of race/ethnicity and whether, and, if so, how, it might need to be adjusted to better address the caregiving situations of particular groups.

We will use the technique of constant comparison¹²⁷ to analyze the qualitative evaluation data gathered from Tele-Savvy participants (at a point four-months after participation). Co-PI [name] and the project coordinator will independently read the transcripts from the first few cohorts, identifying codes that indicate unique observations expressed by participants as well as topics and broader themes around which various codes might cluster. They will compare codes and themes to arrive at mutually agreed upon revisions/refinements in the developing coding scheme ([name] will adjudicate any unresolvable disagreements) and then apply the scheme to transcripts over the course of the project. As significant new themes are identified, previously coded transcripts will be re-read, applying the revised scheme.

Limitations and Challenges. Our decision to limit participation to caregivers with computers and internet access is based on our pilot experience. In the ADRC pilot, we required participants to have their own computers and internet connection; we encountered very few problems. Access is not universal among caregivers, so results will not generalize to all caregivers, but, as noted, internet use in the target age groups (middle-aged and older) continues to rise.¹²⁸ We will employ easy-to-use platforms (Vidyo and Canvas) for Tele-Savvy and attention control conditions; both platforms are accessed by a simple click on an email-supplied link. Navigators can train caregivers to use Canvas and technical assistance of navigators will be provided (via phone and e-mail). A navigator will monitor all Tele-Savvy videoconferences to address any technical problems that might arise. We plan to conduct the videoconferences during weekday working hours; this may be a barrier for some eligible caregivers. To address this, we will schedule an occasional program on a weekend or in the evening. While recruitment is always a reasonable concern, our experience with the pilots provides confidence; operating with very little support, we were easily able to recruit 58 caregivers who completed the studies in the course of approximately 18 months. All of the collaborating sites were chosen because their recruitment bases are at least as strong as that at Emory. There were very few dropouts in the pilots among those who actually began the program (<10%); we have used a 25% attrition rate to be conservative in our estimates for our recruitment target.

References

1. Alzheimer's A. 2016 Alzheimer's disease facts and figures. *Alzheimers Dement*. 2016;12(4):459-509.
2. [name] K, Lewis M, Tornatore J, Sherman CW, Bremer KL. The Savvy Caregiver program: the demonstrated effectiveness of a transportable dementia caregiver psychoeducation program. *J Gerontol Nurs*. 2007;33(3):30-36.

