We seek to make an effective psychoeducation program widely available to family caregivers of persons living with Alzheimer's disease and related disorders. Taking advantage of the growing use of and familiarity with the internet by persons of caregiving age, the project will advance us toward that goal. We will test the program in an established context of collaboration among the Outreach, Recruitment, and Education Cores of four NIA-supported Alzheimer's Disease Centers (ADC). We will employ a wait-list randomized design in which 18 blocks of 15 caregivers each will be assigned either to immediate Tele-Savvy participation groups or to attention control or usual care groups that are invited to participate in Tele-Savvy six months after baseline data collection (total n=270). We will pursue 3 aims::

Aim 1. Establish the effectiveness of Tele-Savvy in reducing or retarding the affective impact (burden, depression, anxiety) on caregivers associated with dementia family caregiving

Aim 2. Establish the effectiveness of Tele-Savvy in promoting the quality of life of persons with Alzheimer's (agitation; Quality of Life; affect) whose caregivers are trained by Tele-Savvy

Aim 3. (a) Establish the effectiveness of Tele-Savvy in enhancing caregiver mastery and (b) test the mediating effect of mastery and enactment on Aim 1 & 2 outcomes

We also propose, as an Exploratory Aim, to examine the comparability of the program's efficacy across three racial/ethnic groups (African Americans, Caucasians, and Latino/Hispanics).

Significance and Innovation.

The Landscape. Dementing conditions, including the most prevalent of these, Alzheimer's disease, pose a large and growing problem nationally and worldwide. Unless dramatic breakthroughs occur, the current population of 5.3 million persons living with these conditions will swell to at least 14 million by 2050.¹ These persons are distributed across the landscape, in inner cities, in suburban areas, and in rural America; there is even some evidence that the current and future prevalence of Alzheimer's in rural areas is disproportionate to the rural population's share of the overall population.²⁻⁴ Care for these persons is costly. Total estimated cost of care in 2015 will be \$216 Billion; by 2050, it could exceed \$1 Trillion.¹

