Monthly team videoconferences will be conducted to discuss project progress, recruitment, data collection and analysis, and other issues. The Emory coordinating team will meet weekly. The site co-

investigators and [name] will also meet annually at the ADC Directors' meeting. Additional Data Safety Monitoring Board committee meetings will be held mid-year in years 2 and 3.

Scientific Approach

Design. We aim to enroll 375 subjects in 25 cohorts of 15 subjects each, starting in project month 9 (see project timeline). We expect to enroll, on average, four cohorts per quarter through project year 2 1/2. Recruitment of every 2 cohorts (30 participants total) is scheduled to take place every 6 weeks. We will use a three-arm design with participants randomly assigned on a 2:2:1 ratio to immediate participation in the Tele-Savvy intervention (N=108), immediate participation in an attention control condition (Healthy Living) (N=108), and a usual care condition (N=54). There will be five data-collection points evenly spaced across 12 months. Those in each cohort's intervention condition will take part in Tele-Savvy immediately following baseline data collection. Those in the attention control and usual care conditions will take part in Tele-Savvy after a delay of 6 months (following the 6-month data collection point). Below, we describe the preparation activities in which we will engage (facilitator training and material revisions) and then describe the trial itself. Four NIA-supported Alzheimer's Disease (Research) Centers will collaborate in recruitment, and Emory University will serve as the coordinating center. Emory will be responsible for randomization of subjects (recruits from all sites will be pooled together for randomization), for delivery and fidelity monitoring of the intervention and attention control condition, and for all data gathering and analysis.

Please see the added document for Amendment 8.

Project Timeline, by Quarters

Main Project Activities	Year 1				Year 2				Year 3				Year 4			
	1	2	3	4	1	2	3	4	1	2	3	4	1	2	3	4
Staffing; Training; Finalizing																
DSMB scheduled meetings		X			X				X				X			X
Enroll 18 cohorts (15 each) + Acquisition	30	60	90	120	150	180	210	240	270							
Data Collection																
Data Cleaning and Analysis																
Dissemination																

Preparation.

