meta-analyses. With a final expected sample size of 215 (86, 86, 54 in Tele-Savvy (TS), attention control (AC), and usual care (UC) groups respectively), for the primary intervention test (group-by-time effect) comparing the outcomes of the three group changes from T1 to T2 to T3 (3-by-3 repeated measures design of three groups measured at three time points), at 80% power and 5% significance level, small-to-moderate effect sizes, Cohen's $f = 0.21-0.24$ may be detected for the main effects for group, time and group-by-time interaction effects (given moderate correlation between measurement pairs of $r=0.3-0.5$) (power analysis using PASS 14 Power Analysis and Sample Size Software (2015). NCSS, LLC. Kaysville, Utah, USA, ncss.com/software/pass). After adjusting for any potential group differences, the overall intervention effect of the Tele-Savvy program for the combined T1-to-T3 pre-post effects for the immediate Tele-Savvy group plus the T3-to-T5 pre-post effects from the AC and UC groups will yield a total estimated 215 subjects to perform a pre-post test to detect a small effect size of $d=0.19$ at 80% power and 5% significance level. With the pooled sample, we will be able to also test the mediating effects of mastery and self-efficacy on the Tele-Savvy program for the caregiver outcomes. As shown by Fritz and MacKinnon (2007), sample sizes of 148-196 were adequate to achieve 80% power to detect small-to-moderate effect sizes for the indirect effect of the independent variable on the dependent variable through the mediating variable considering both the Sobel test as well as percentile and bias-corrected bootstrapped approaches.¹⁰⁸ Although our analytic strategy is robust to missing data we will enroll 270 CGs (108 for TS and AC groups and 54 for UC group) per consideration 1 above (maximize accommodation) allowing for an expected 20% attrition. For the exploratory aim comparing the program's efficacy across the 3 ethnicity groups, with an expected final sample size of 215 subjects and proportions of approximately 65% Caucasian, 20% African American, 15% Hispanic, at 80% and 5% level of significance, we will be able to detect moderate effect sizes Cohen's $f=0.19-0.23$ (for 3-group by 2-time point RM-ANOVA for group, time and group-by-time effects).

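### The current text gives two enrolment targets (375 and 270), final arms that sum to 226 instead of 215, and two allocation rules (2:2:1 and equal numbers)

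*Combined protocol and SAP*

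**What the plan says.** **Enrolment.** The Design paragraph under Scientific Approach states "We aim to enroll 375 subjects in 25 cohorts of 15 subjects each". The same paragraph has participants "randomly assigned on a 2:2:1 ratio to immediate participation in the Tele-Savvy intervention (N=108", with 108 in attention control and 54 in usual care. It ends with "Please see the added document for Amendment 8". The Project Timeline below it has the row "Enroll 18 cohorts (15 each) + Acquisition", which ends at 270. The Aims section plans "18 blocks of 15 caregivers each will be assigned either to immediate Tele-Savvy participation groups", total 270. The Power Analysis section says "we will enroll 270 CGs (108 for TS and AC groups and 54 for UC group".

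**Final sample.** The Power Analysis section begins "With a final expected sample size of 215 (86, 86, 54 in Tele-Savvy (TS". It attaches d=0.19 (pooled pre-post test) and f=0.21-0.24 (three groups by three time points) to 215 subjects, at 80% power and 5% significance, and it expects 20% attrition.

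**Allocation.** The Design section gives 2:2:1. The section on Subject Randomization, Coordination, and Retention instead has the statistician use blocks to put the same number from each cohort of 15 into each of the three conditions. It then says that caregivers best served by a Saturday or evening program form a block randomised to Tele-Savvy or attention control. Usual care is not named for them.

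**Attrition.** Limitations and Challenges says that a 25% rate was used for the recruitment target.

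**The concern.** The enrolment target, the arm sizes and the allocation ratio are the figures that recruiters, the statistician and the monitoring board work from. Each appears in two forms in text that is current, so this is not a difference between an amendment log and the plan.

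Allocation matters most for conduct. The section that instructs the statistician gives a rule which, if followed, produces arms that the documents state nowhere. The ratio also sets how precisely Tele-Savvy is compared with each control. The enrolment conflict leaves a reader unable to say which number the stated detectable effects go with. The arm sum matters less, but it sits in the sentence that carries the sample size.

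**Working it through.** **1. Enrolment target**

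- Design sentence: 25 × 15 = 375.
- Arms in the same paragraph: 108 + 108 + 54 = 270.
- Timeline and Aims: 18 × 15 = 270.
- Gap: 375 − 270 = 105 caregivers, or 105/15 = 7 cohorts.

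**2. Final sample**

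- Listed arms: 86 + 86 + 54 = 226, not 215.
- Applying 20% loss to each arm: 0.8 × 108 = 86.4 and 0.8 × 54 = 43.2, so 86 + 86 + 43 = 215.
- The 54 is therefore the enrolled usual-care number, carried over without the loss.

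To see which total the power figures belong to, I reproduced them at two-sided 5% (sidedness is not stated) and 80% power:

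- Paired d ≈ (1.960 + 0.842)/√N. At N=215 this is 2.802/14.663 = 0.191 (0.192 by the noncentral t), the stated 0.19.
- f from the noncentral F with λ = N·f² and degrees of freedom (2, N−3), (2, 2(N−3)) and (4, 2(N−3)). The plan does not print its formula; this form returns its range.

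| Analysed N | d | f group | f time | f group-by-time |
|---|---|---|---|---|
| 215 | 0.192 | 0.213 | 0.212 | 0.237 |
| 226 | 0.187 | 0.208 | 0.207 | 0.231 |
| 281 (375 less 25%) | 0.168 | 0.186 | 0.186 | 0.207 |
| 300 (375 less 20%) | 0.162 | 0.180 | 0.180 | 0.200 |

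The stated 0.21-0.24 matches 215. At 226 the upper end would round to 0.23. So the total of 215 is the intended one and the 54 is the slip.

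**3. Allocation**

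- 2:2:1 in a cohort of 15: 6/6/3. Over 18 cohorts: 108/108/54, as stated.
- Equal numbers in a cohort of 15: 5/5/5. Over 18 cohorts: 90/90/90, stated nowhere.
- A Saturday or evening block that excludes usual care departs from 6/6/3, so the stated totals need 2:2:1 in every block. The size and number of such blocks are not given, so I put no figure on the effect.

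For scale, take an unadjusted two-group comparison at one time point after 20% loss from 270, solving for d at 80% power with noncentrality d/√(1/n₁ + 1/n₂):

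| Rule | Against attention control | Against usual care |
|---|---|---|
| 2:2:1 | 86 vs 86: d=0.43 | 86 vs 43: d=0.53 |
| Equal (0.8 × 90 = 72) | 72 vs 72: d=0.47 | 72 vs 72: d=0.47 |

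**4. Attrition (minor)**

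- 270 less 20% is 216; 270 less 25% is 202.5.
- The 25% may be loose wording: 216 × 1.25 = 270, the same enrolment that a 20% loss implies.

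**The case against.** The best defence is that Amendment 8 is cited at the point where 375 appears and is not among the documents supplied. It may justify 375, revise the arms and restate the power. That stands, and nobody should say that 375 has no justification. It does not remove the conflict, because the paragraph's own arms still do not sum to its own total, and the Aims, timeline and power section still say 270.

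A reader might infer that the trial is underpowered, or that its power calculation is wrong. The documents do not support this: d and f reproduce at 215, and 215 follows from 270 with 20% loss.

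A reader might equally infer that at 375 the trial will certainly detect smaller effects than stated. That is not supported either. The power figures attach to subjects analysed, and no loss rate is given for 375. If 375 had been adopted to offset heavier loss, 215 could still be the analysed number (1 − 215/375, about 43% loss) and the stated figures would stand.

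It can also be said that the reference to an eighth amendment suggests the trial was already under way, so writing 2:2:1 into the randomisation section could misdescribe what was done. That is fair, and the fix below allows for it. Finally, the two-group d values are not the planned three-group longitudinal model. They show direction and rough size only.

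**Conclusion.** The inconsistencies are real and should be fixed. The enrolment target differs by 105 caregivers (7 cohorts). The final usual-care arm is printed as 54 where 43 is needed to reach 215; this is a wrong arm figure with no material effect on the detectable effects. The allocation rule is stated in two incompatible ways, giving 108/108/54 or 90/90/90 over 270, and the Saturday or evening provision fits neither three-arm rule. In the simple illustration, moving from 2:2:1 to equal arms changes the detectable d from 0.43 to 0.47 against attention control and from 0.53 to 0.47 against usual care.

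The sums need no assumption beyond the plan's own figures. The reproduction of d and f assumes a two-sided test and the λ = N·f² form. The illustration assumes 270 enrolled and 20% loss in every arm. Which target and which allocation were actually used cannot be settled from the documents supplied.

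**What to change.** - **Target.** State one enrolment figure and carry it through the Aims, the Design paragraph (total and arms), the timeline row and the Power Analysis section. Say in the body text what Amendment 8 changed.
- **If 270 is kept.** Change the final usual-care arm from 54 to 43. The stated d and f stand.
- **If 375 is the target.** State its arms, the assumed loss and the resulting analysed number, and restate d and f for that number. For example, d=0.16 and f=0.18-0.20 at 300 (20% loss), or d=0.17 and f=0.19-0.21 at 281 (25% loss). If only 215 are to be analysed, say so and keep the present figures.
- **Allocation.** In the randomisation section, replace the equal-numbers wording with 2:2:1 (6/6/3 per cohort of 15), the only ratio that matches the stated arms. If any cohort was already randomised otherwise, state the ratio actually used and correct the arm totals.
- **Saturday and evening blocks.** State whether they can be assigned to usual care, and make the arm totals agree.
- **Attrition.** Use one rate in the Power Analysis and Limitations sections.

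The cost is protocol wording, a check of the randomisation records if cohorts have already been assigned, and one rerun of the power calculation if the analysed number changes. No subjects are needed beyond whichever stated target is kept.
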